10.0 Safety Analysis

10.1 General Considerations

Comparisons between treatment groups (Studies M15-562/M15-563) of interest will not be performed.

All other safety assessments that are taken no more than 45 days after the last dose of study drug will be included in the safety evaluation of the Treatment Period, and all safety assessments that are taken more than 45 days but not more than 20 weeks after the last dose of study drug will be included in the safety evaluation for the Post-treatment Follow-up Visit.

10.2 Analysis of Adverse Events

The Stand-Alone data set will be the primary data set for adverse event summaries. Analyses that will also be performed on the Cumulative data set are as follows: adverse event overview, adverse event incidence by system organ class (SOC) and preferred term, adverse event incidence in descending frequency by overall subjects, and SAE incidence by SOC and preferred term.

All adverse events will be coded using the most current version of the Medical Dictionary for Regulatory Activities (MedDRA). A treatment-emergent adverse event (TEAE) is defined as any adverse event that begins or worsens in severity on or after the first study drug dose date and no more than 20 weeks after the last study drug dose date. Analysis of adverse events will also be conducted by geographical region (North America including US and Canada, European countries plus Australia, and Japan).

10.2.1 Adverse Event Overview

The number and percentage of subjects experiencing one or more adverse events in the following adverse event categories will be summarized for each treatment group and overall subjects in both Stand-Alone data set and the Cumulative data set. No comparisons of treatment groups will be performed.

- Any TEAE
- Any TEAE that was rated reasonable possibility of being related to study drug by the investigator
- Any severe TEAE
- Any serious TEAE
- Any TEAE that led to discontinuation of study drug
- Any fatal TEAE
- All deaths

10.2.2 Adverse Event Incidence

TEAE incidence will be summarized and presented using primary MedDRA system organ classes (SOCs) and preferred terms (PTs). The system organ classes will be presented in alphabetical order and the preferred terms will be presented in the alphabetical order within each system organ class. Subjects reporting more than one adverse event for a given MedDRA PT will be counted only once for that term. Subjects reporting more than one adverse event within a SOC will be counted only once for the SOC total. Subjects reporting more than one adverse event will be counted only once in the overall adverse event total.

The number and percentage of subjects experiencing one or more TEAEs will be summarized by PT for each treatment group and overall subjects. The PTs will be presented by decreasing frequency in overall subjects.

The number and percentage of subjects experiencing one or more adverse events in the following adverse event categories will be summarized by primary SOC and PT for each treatment group and overall subjects.

- Any TEAE
- Any serious TEAE
- Any TEAE that led to discontinuation of study drug
- Any TEAE assessed by the investigator to be Reasonable Possibility of Being Related to study drug

The number of subjects experiencing one or more TEAEs will also be summarized by maximum severity category (mild, moderate, severe and unknown) and primary SOC and PT for each treatment group and overall subjects. Subjects reporting more than one TEAE for a given PT will be counted only once for that term in the most severe category reported. If a subject has an adverse event with unknown severity, then the subject will be counted in the severity category of "unknown" even if the subject has another occurrence of the same event with a severity present. The only exception is if the

subject has another occurrence of the same adverse event with the most extreme severity – "Severe." In this case, the subject will be counted under the "Severe" category. No comparisons of treatment groups will be performed.

The number of subjects experiencing one or more TEAEs will also be summarized by maximum relationship category (Reasonable Possibility of Being Related, No Reasonable Possibility of Being Related and Unknown), as assessed by the investigator, and primary SOC and PT for each treatment group and overall subjects. Subjects reporting more than one TEAE for a given PT will be counted only once for that term in the most related category reported. If a subject has an adverse event with unknown relationship, then the subject will be counted in the relationship category of "unknown," even if the subject has another occurrence of the same event with a relationship present. The only exception is that if a subject has another occurrence of the same adverse event with a relationship assessment of "Reasonable Possibility of Being Related." In this case, the subject will be counted under the "Reasonable Possibility of Being Related." No comparisons between treatment groups will be performed.

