Adverse events will be coded using the current version of the Medical Dictionary for Regulatory Activities (MedDRA). The number and percentage of subjects with treatment-emergent adverse events will be tabulated by MedDRA System Organ Class (SOC) and Preferred Term with a breakdown by treatment sequence in Studies M15-562/M15-563: 2000/2000 mg, 4000/4000 mg, placebo/2000 mg, and placebo/4000 mg. Tabulations will also be provided by rating of severity (mild, moderate, and severe) and by whether possibly related to study drug. The number and percentage of subjects experiencing treatment-emergent SAEs (including deaths) and adverse events leading to premature discontinuation of study drug will be tabulated according to the MedDRA SOC and preferred term by treatment group. The number and percentage of subjects with laboratory test values and measurements on vital signs that are potentially clinically significant, according to predefined criteria, will be tabulated as well. The percentage of subjects who have suicidal behavior, suicidal ideation only, and suicidal behavior or ideation from the C-SSRS assessment will be summarized by treatment sequence.

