6.1.3 Relationship to Study Drug

The investigator will use the following definitions to assess the relationship of the adverse event to the use of study drug:

Reasonable Possibility	After consideration of factors including timing of the event, biologic plausibility, clinical judgment, and potential alternative causes, there is sufficient evidence (information) to suggest a causal relationship.
No Reasonable Possibility	After consideration of factors including timing of the event, biologic plausibility, clinical judgment, and potential alternative causes, there is insufficient evidence (information) to suggest a causal relationship.

For causality assessments, events assessed as having a reasonable possibility of being related to the study drug will be considered "associated." Events assessed as having no reasonable possibility of being related to study drug will be considered "not associated." In addition, when the investigator has not reported a causality or deemed it not assessable, AbbVie will consider the event associated.

If an investigator's opinion of no reasonable possibility of being related to study drug is given, an "Other" cause of event must be provided by the investigator for the SAE.

[figure not shown]

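### The protocol treats adverse events with missing or not-assessable causality as associated with study drug, but the SAP's three related-TEAE outputs leave them out

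*SAP*

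**What the plan says.** **Protocol.** Section 6.1.3 gives the investigator two causality ratings, reasonable possibility and no reasonable possibility, which map to associated and not associated. It then covers the remaining case: "when the investigator has not reported a causality or deemed it not assessable, AbbVie will consider the event associated". The rule sits in the general causality definitions and is not limited there to serious events or expedited reporting. The synopsis (1.2) plans AE tables on the same axis: "Tabulations will also be provided by rating of severity (mild, moderate, and severe) and by whether possibly related to study drug".

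**SAP.** Three outputs report related TEAEs, all tied to the investigator's rating:

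- Overview (10.2.1): "Any TEAE that was rated reasonable possibility of being related to study drug by the investigator".
- Incidence by SOC and PT (10.2.2): "Any TEAE assessed by the investigator to be Reasonable Possibility of Being Related to study drug".
- List of subject numbers by PT (10.2.3): again limited to TEAEs the investigator assessed as a reasonable possibility.

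A fourth output, the maximum-relationship table in 10.2.2, has three investigator-assessed categories: Reasonable Possibility, No Reasonable Possibility and Unknown. There, "If a subject has an adverse event with unknown relationship, then the subject will be counted in the relationship category of" unknown, even when another occurrence of the same event carries a rating. "The only exception is that if a subject has another occurrence of the same adverse event with a relationship assessment of" reasonable possibility; such a subject is counted as related.

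Nothing in the SAP maps unknown causality to related or refers to the protocol convention.

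**The concern.** The two documents apply different rules to the same records. The protocol closes the gap left by a missing rating in the cautious direction. The SAP opens a third category and keeps it out of every output that is specifically about related events. As planned, no AE table or listing applies the protocol's rule directly.

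This matters because long-term safety and tolerability is a primary objective. SAP section 9.0 says no efficacy analyses will be conducted, and section 10.1 says no safety comparisons between groups will be made. The descriptive AE tables therefore carry much of what the study will report, and related TEAEs are the second line of the overview. A reader who knows protocol 6.1.3 would expect that line to include events with no causality recorded. It will not.

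**Working it through.** The documents state no figure for this point, so there is nothing to reproduce. The check compares the two rules over every case they can meet.

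**Inputs.** For one subject and one PT, each occurrence is R (reasonable possibility), N (no reasonable possibility) or U (unknown). The SAP does not define unknown. Since the protocol offers only two ratings, I read U as missing or not assessable.

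**Rules.**

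- SAP related outputs (10.2.1 to 10.2.3): included if the set contains R.
- SAP maximum-relationship table (10.2.2): R if the set contains R; otherwise Unknown if it contains U; otherwise N.
- Protocol 6.1.3: associated if the set contains R or U.

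| Ratings present | SAP related outputs | SAP maximum-relationship category | Protocol 6.1.3 |
|---|---|---|---|
| R | in | Reasonable Possibility | associated |
| N | out | No Reasonable Possibility | not associated |
| U | **out** | Unknown | **associated** |
| R, N | in | Reasonable Possibility | associated |
| R, U | in | Reasonable Possibility | associated |
| N, U | **out** | Unknown | **associated** |
| R, N, U | in | Reasonable Possibility | associated |

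**Direction.** The rules disagree in 2 of the 7 combinations, U alone and N with U. In both, the protocol includes the subject and the SAP does not. No combination goes the other way, so the SAP count is at most the protocol count.

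**Recoverability.** Both discordant combinations land in Unknown. By PT, therefore, Reasonable Possibility + Unknown = the protocol's associated count. The SAP states this precedence for a given PT only; at SOC and overall level the identity holds only if the same precedence is applied there. Section 10.2 also does not name the maximum-relationship table among the analyses run on the Cumulative data set, although the overview is run on it.

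**Level of counting.** In the overview, a subject is missed only if at least one TEAE has unknown causality and no TEAE of any kind is rated R. At PT level, a subject is missed for that PT even if a different PT is rated R.

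**Size.** The number of affected subjects, k, is not in the documents and is assumed here. The denominator is 378, the most that can enrol (SAP 4.3). Shift in the overview row = 100 × k / 378:

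- k = 0: 0
- k = 1: 0.26 percentage points
- k = 5: 1.32
- k = 10: 2.65
- k = 20: 5.29

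With fewer than 378 enrolled, each subject weighs more.

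**The case against.** **Different assessors.** The protocol sentence says how the sponsor will classify an event; the SAP outputs are labelled as the investigator's assessment. Elsewhere the protocol separates the two (6.1.7 and 6.1.7.5 speak of judgement by the investigator or the sponsor), and its AE analysis section (8.1.2.2) has no rule for missing causality. This is the strongest point and part of it stands: a table of investigator ratings that shows a missing rating as unknown is accurate as labelled, and recoding under that label would report ratings nobody gave. It does not remove the conflict. The SAP never draws the distinction and plans no output under the sponsor's convention. Protocol 6.1.5 was not in the text reviewed, so the rule's scope could not be checked against it.

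**The information is kept.** This stands by PT, as shown above. The SAP also ranks Unknown above No Reasonable Possibility, which is already cautious. The gap is confined to the overview row, the related SOC/PT table and the list.

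**It may never arise.** Protocol 6.1 has the investigator record relationship for every event, and section 10.2 has eCRFs reviewed for completeness. Missing causality could well be rare.

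**Limited consequence.** All subjects receive active drug, and no test or decision rule in the SAP uses this count. That holds, and it limits the weight of the point.

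**Conclusion.** The inconsistency is real and should be resolved. Protocol 6.1.3 counts missing or not-assessable causality as associated; the three related-TEAE outputs in SAP 10.2.1 to 10.2.3 do not, and any difference can only lower their counts relative to the protocol's rule.

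A reader might infer that drug-related events will be under-counted in this study. The documents do not support that as a statement of fact. The shortfall is measured against the protocol's own convention and arises only if some TEAE has missing or not-assessable causality and the same subject has no qualifying reasonable-possibility rating. No rate is given, so no number of affected subjects can be claimed; the percentages above only convert assumed counts. Nor does the SAP conceal such events, since they remain visible as Unknown and the protocol count can be rebuilt by PT.

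The conclusion rests on two readings: that Unknown means missing or not assessable, and that 6.1.3 applies to AE tabulation because it carries no stated limit.

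**What to change.** In SAP 10.2.1 to 10.2.3, count a missing or not-assessable relationship as associated in the overview row, the related SOC/PT table and the related-PT list. Relabel these outputs as the protocol 6.1.3 convention (investigator-rated reasonable possibility, or causality missing or not assessable), so that no rating is attributed to an investigator who did not give it. Footnote the number of events and subjects included by this rule. Leave the Unknown category in the maximum-relationship table so that the missingness stays visible.

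If investigator-only outputs are intended, the SAP should say so, justify departing from 6.1.3, and add one row under the sponsor's convention. It would also help to say which rule governs the related-AE item among the DMC outputs in SAP 4.4, which is silent on missing causality.

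The cost is one derivation rule, or one added row, plus changed labels and footnotes. The reported related-AE rate may become slightly less favourable.

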10.2.3 Listing of Adverse Events

The following additional summaries of adverse events will be prepared only on Stand-Alone data set.

- List of subject numbers associated with each PT for all TEAEs
- List of subject numbers associated with each PT for all TEAEs assessed by the investigator as Reasonable Possibility of Being Related.
- Listing of all serious adverse events
- Listing of all adverse events that led to discontinuation of study drug
- Listing of all fatal adverse events
- Listing of all deaths

10.3 Analysis of Laboratory Tests

Analyses of Laboratory tests will be performed on the Stand-Alone data set.

The laboratory tests are described in the following table.

Table 1. Laboratory tests

Hematology	Clinical Chemistry	Urinalysis
Hematocrit	Blood urea nitrogen (BUN)	Specific gravity
Hemoglobin	Creatinine	pH
Red blood cell (RBC) count	Total bilirubin	
White blood cell (WBC) count	Albumin	
Neutrophils	Aspartate aminotransferase (AST)	
Bands (if detected)	Alanine aminotransferase (ALT)	
Lymphocytes	Alkaline phosphatase	
Monocytes	Sodium	
Basophils (if detected)	Potassium	
Eosinophils (if detected)	Calcium	
Platelet count (estimate not acceptable)	Inorganic phosphate	
Mean corpuscular volume (MCV)	Uric acid	
Mean corpuscular hemoglobin concentration (MCHC)	Cholesterol	
Prothrombin time (PT)	Total protein	
Activated partial thromboplastin time (aPTT)	Glucose	
PT/INR (Prothrombin Time/International Normalized Ratio)	Triglycerides	
	Bicarbonate/Carbon Dioxide (CO ₂) Chloride	

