5.3.1.1.10 Clinical Laboratory Tests

Samples will be obtained at a minimum for the clinical laboratory tests listed in [Table 2](#) at the times indicated in the Study Activities Table ([Appendix C](#)).

A certified laboratory will be used to process and provide results for the clinical laboratory tests. Central Laboratory reference ranges will be provided prior to initiation of the study. The baseline laboratory test results for clinical assessment for a particular test will be defined as the last measurement prior to the initial dose of study drug.

Table 2. Clinical Laboratory Tests

Hematology	Clinical Chemistry	Urinalysis
Hematocrit	BUN	Specific gravity
Hemoglobin	Creatinine	Ketones
RBC count	Total bilirubin	pH
WBC count	Albumin	Protein
Neutrophils	AST	Glucose
Bands (if detected)	ALT	Blood
Lymphocytes	ALP	Microscopic examination, if dipstick results are positive
Monocytes	Sodium	CSF Basic Laboratory Tests^c
Basophils (if detected)	Potassium	
Eosinophils (if detected)	Calcium	RBC, WBC with differential
Platelet count (estimate not acceptable) ^a	Inorganic phosphate	Total protein
MCV	Uric acid	Albumin
MCHC	Cholesterol	Glucose
PT	Total protein	
aPTT ^b	Glucose	
PT/INR ^b	Triglycerides	
	Bicarbonate/CO ₂ chloride	

ALP = alkaline phosphatase; ALT = alanine aminotransferase; aPTT = activated partial thromboplastin time; AST = aspartate aminotransferase; BUN = blood urea nitrogen; CSF = cerebrospinal fluid; CO₂ = carbon dioxide; INR = international normalized ratio; MCHC = mean corpuscular hemoglobin concentration; MCV = mean corpuscular volume; PT = prothrombin time; RBC = red blood cell; WBC = white blood cell

- Platelet count results to be reviewed by the investigator before lumbar puncture.
- Coagulation results to be reviewed by the investigator before lumbar puncture.
- To be done at the local laboratory. If the local laboratory is unable to perform some of the CSF measurements, samples may be sent to the central laboratory for analyses of total protein, albumin, and glucose only.

For any laboratory test value outside the reference range that the investigator considers to be clinically significant:

- The investigator will repeat the test to verify the out-of-range value.
- The investigator will follow the out-of-range value to a satisfactory clinical resolution.
- A laboratory test value that requires a subject to be discontinued from the study or requires a subject to receive treatment will be recorded as an adverse event.

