5.3.1.1.12 Lumbar Puncture

Lumbar punctures to collect CSF will be performed on all subjects at the times indicated in the Study Activities Table ([Appendix C](#)). Lumbar puncture on Day 1 and lumbar puncture at completion (Week 260) or premature discontinuation should only be done if at least 3 months have elapsed since the previous lumbar puncture.

A sample of CSF will be collected according to the Collection and Processing of CSF Samples manual provided to the study site by the Sponsor. If sampling is not successful or is standard of care for the institution, other methods including CT/fluoro guided or ultrasound guided lumbar puncture can be used at the discretion of the local clinical site staff. CSF clinical laboratory tests will be analyzed locally at the applicable clinical site after each lumbar puncture/CSF collection. These measures include cell counts (RBC and WBC with differential), total protein, albumin, and glucose (Refer to [Table 2](#) for Clinical Laboratory Tests). If the local laboratory is unable to perform some of the CSF measurements, samples may be sent to the central laboratory for analyses of total protein, albumin, and glucose only. Other CSF measurements (e.g., ABBV-8E12 concentration, tau, and other exploratory biomarkers) will be analyzed by the applicable designated laboratory or at AbbVie.

Subjects who are not able to undergo an LP may be enrolled with permission of the AbbVie TA MD without the requirement of an LP during the study.

Headaches may occur following withdrawal of CSF. Subjects may be treated with the following: IV hydration, IV caffeine administration, bed-rest, and analgesics.

Uncommonly a blood patch (injection of some of the subject's blood to patch the CSF leak) may be needed. Potential but rare risks of lumbar puncture include infection, damage to nerves in the back, and bleeding into the CSF space. The risk of these is much less than 1%.¹¹ Institutional policy and investigator discretion should be followed to provide the appropriate post-lumbar puncture observation period, and to provide information to the subject on possible side effects and limitations on strenuous physical activity and driving.

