10.3.1 Analysis of Mean Changes for Laboratory Tests

The following summaries of laboratory data will be included in the output: mean change from baseline to each double-blind visit value and to the minimum, maximum and final double-blind value for each continuous hematology, chemistry and urinalysis variable, mean change from final double-blind value to final post-treatment value presented for each continuous hematology, chemistry and urinalysis variable, shift tables, and potentially clinically significant laboratory values.

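### SAP Table 1 leaves out the CSF safety panel and five urinalysis lines of Protocol Table 2, and no SAP output names the CSF panel

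*SAP*

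**What the plan says.** Protocol 5.3.1.1.10 (Table 2) sets out the clinical laboratory tests. Beside hematology, chemistry and urinalysis it has a block headed "CSF Basic Laboratory Tests", with the footnote "To be done at the local laboratory". The central laboratory may take over protein, albumin and glucose if the site cannot run them. Protocol 5.3.1.1.12 has the panel run after every lumbar puncture: "These measures include cell counts (RBC and WBC with differential), total protein, albumin, and glucose". The same paragraph treats drug concentration, tau and exploratory markers as a separate set of CSF measurements. The urinalysis column of Table 2 has seven lines, ending with "Microscopic examination, if dipstick results are positive".

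SAP 10.3 says "The laboratory tests are described in the following table". Its Table 1 has a urinalysis column of two lines, "Specific gravity" and pH, and no CSF block. SAP 10.3.1 reports mean changes "for each continuous hematology, chemistry and urinalysis variable". SAP 10.3.2 limits shift tables to the same three families. SAP 10.3.3 relies on the potentially clinically significant (PCS) criteria in Appendix A, which has no CSF or urine criterion.

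Protocol 8.1.2.3, the protocol's own laboratory analysis section, is also confined to hematology, chemistry and urinalysis.

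**The concern.** Long-term safety is the first primary objective in both documents, and SAP 4.6 names laboratory abnormalities as a safety variable. The protocol describes the brain as the only organ that appears to express tau at significant levels (6.1.7.2) and asks for close monitoring for neurotoxicity (6.1.7.5). A CSF cell count and protein is a direct laboratory look at that compartment, and it is obtained by an invasive procedure whose risks the protocol lists.

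A programmer working from SAP Table 1 would produce no CSF safety table and no output for urine protein or blood. A modest, asymptomatic shift in CSF white cells or protein across a treatment group is the kind of signal that only a group summary shows. As planned, it could go unseen in the study report.

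**Working it through.** There is no power or error-rate figure to reproduce. The check compares two lists and then searches for any other output that would cover the difference.

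**Step 1. Line-by-line comparison of Protocol Table 2 with SAP Table 1.**

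| Block | Protocol Table 2 | SAP Table 1 | Missing from SAP |
|---|---|---|---|
| Hematology | 16 | 16 | none |
| Chemistry | 17 | 17 | none |
| Urinalysis | 7 | 2 | ketones, protein, glucose, blood, microscopy |
| CSF | 4 | 0 | RBC and WBC with differential, total protein, albumin, glucose |
| Total | 44 | 35 | 9 |

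Totals: 16 + 17 + 7 + 4 = 44; 16 + 17 + 2 + 0 = 35; 44 − 35 = 9.

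**Step 2. Search of the other SAP outputs for the CSF panel.**

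- 10.3.1 and 10.3.2: hematology, chemistry and urinalysis only.
- 10.3.3 and Appendix A: no CSF criterion, so nothing reaches the PCS table or listing.
- 10.6.2: MRI findings, which are imaging.
- 11.0: drug concentration in serum and CSF.
- 12.1 and 12.2: tau and imaging variables. 12.2 closes with a general promise to describe other reported variables. It sits in the biomarker section, while Protocol 5.3.1.1.12 keeps this panel apart from the biomarkers.

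**Step 3. Adverse-event route.** Under Protocol 6.1.1.1 a laboratory abnormality is an adverse event only if it leads to discontinuation, needs intervention, meets an Appendix D PCS criterion, or is judged one by the investigator. Appendix D has no CSF criterion. The rule in 5.3.1.1.10 to report an event or document why not is therefore never triggered by a CSF value. Only the other conditions remain, and the resulting tables count event terms, not CSF values.

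**Step 4. Volume of data.** Year 1 has two scheduled post-baseline punctures, at Weeks 24 and 52. If all 378 subjects of Study M15-562 enrolled and had both, there would be 378 × 2 = 756 panels. This is a ceiling: 5.3.1.1.12 allows enrolment without any puncture, Table 1 of the protocol lists anticoagulants as exclusionary for puncture, and there will be attrition.

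**Step 5. What a summary could exclude.** With zero events among n subjects, the one-sided 95% upper bound is 1 − 0.05^(1/n). The documents give no group sizes, so n must be assumed. Assuming equal allocation in Study M15-562 and full rollover, a continuing-dose group has 378/3 = 126 subjects and a former-placebo group has 126/2 = 63.

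- n = 126: 1 − 0.05^(1/126) = 2.35%.
- n = 63: 1 − 0.05^(1/63) = 4.6%.

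Fewer punctured subjects would widen both bounds.

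**The case against.** The strongest reply is that the SAP withdraws nothing the protocol promised. Protocol Table 2 is a collection list. The analysis section, 8.1.2.3, promises changes only for continuous hematology, chemistry and urinalysis parameters and PCS summaries only for hematology and chemistry. Specific gravity and pH are plausibly the continuous urine parameters, and low/normal/high shift tables do not fit graded dipstick results naturally. This stands, and it makes the gap one of both documents. It does not close it: the data are still collected with no planned output.

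Second, other safeguards exist. Investigators must mark out-of-range values as clinically significant or not, and must repeat and follow those they consider significant. Values needing treatment or discontinuation become adverse events, and the DMC may see all data it needs. A clinically important case therefore has a route into the report. Values below that level have none.

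Third, MRI covers the brain earlier. The first post-baseline scan is at Week 12 and the first post-baseline puncture at Week 24, and SAP 10.6.2 tabulates edema, hemorrhage and white matter change. A reader might infer that CSF is the only or the earliest sign of CNS inflammation in this study. The documents do not say so, and the schedule argues against earliest.

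Fourth, local results are harder to pool. That is a real cost, but SAP 10.3.2 already classifies each value against the range of the laboratory that ran it.

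**Conclusion.** The omission is real: 9 of 44 listed laboratory lines, including the whole CSF safety panel, have no place in SAP Table 1, and no SAP output names the CSF panel. It is a safety-reporting gap worth closing. It does not threaten the validity of the trial.

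Three stronger readings should be resisted. A reader might infer that all urine dipstick results are gone, but specific gravity and pH are kept. A reader might infer that the SAP breaks a protocol commitment on CSF, but Protocol 8.1.2.3 makes none. A reader might quote a bound of about 2.4% as what the plan forfeits. That figure rests on an assumed 126 subjects per group, all punctured. It becomes about 4.6% at 63, and the SAP specifies no such bound for any safety event. No precision figure should be quoted without its assumed group size.

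The conclusion assumes that Table 1 is read as a closed list and that the general sentence in SAP 12.2 is read where it stands, as applying to biomarkers.

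**What to change.** Add to SAP 10.3 and Table 1:

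- **CSF panel:** a descriptive summary of WBC, RBC, total protein, albumin and glucose by treatment group and scheduled puncture. Give the value, the change from the Stand-Alone baseline where available, and the number and percentage outside the performing laboratory's range, as 10.3.2 already does for other tests. Add a listing of abnormal values.
- **Urine:** baseline-to-worst category shifts for protein, blood, glucose and ketones.

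If the sponsor prefers not to report any of these, the SAP should say so and why.

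For subjects already on ABBV-8E12 in Study M15-562, the Stand-Alone baseline is an on-drug value, so their change tables show only further change. A table footnote should say this.

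The CSF/serum albumin ratio and a flag for traumatic taps are optional extras.

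The cost is a few descriptive tables and a listing from data already collected, plus standardising local units and ranges. Puncture waivers and attrition will thin the later visits, so each table should show the number of subjects contributing.
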